1. The primary outcome of this study will be patient discomfort related to BTX-A injection.
2. This will be measured using a validated 11 point (0-10) pain scale – the Numeric Pain Scale (NPS). Patients will rate their discomfort via the NPS prior to and after injections. The measurement for comparison will be the difference in those values.

Secondary Outcomes:

1. Efficacy and patient satisfaction will be evaluated using the Overactive Bladder Symptom and Health-Related Quality of Life Short-Form (OAB-q SF) validated questionnaire.¹⁵ The OAB-q SF is a condition-specific questionnaire developed to assess the symptom bother and health related quality of life (HRQL) impact of OAB. The form asks patients to detail their level of bother related to their bladder symptoms and how those symptoms have affected their lives in the last four weeks. There are 19 questions in total and answers are recorded by checking a box from 1-6. Raw scores are then transferred to a 0-100 scale using formulas provided in the validation literature.¹⁵

2. Procedure time will be recorded from the start of cystoscope insertion to cystoscope removal and procedure end.
3. Symptomatic urinary tract infection (UTI) within the first 30 days after the procedure will be recorded. Symptomatic UTI will be defined as positive nitrites or leukocyte esterase on urine dip or positive urine culture in addition to the presence of dysuria, hematuria, or urinary frequency/urgency in the 30 days after the procedure
4. Rate of bothersome incomplete bladder emptying requiring catheterization within the first 30 days of the procedure
5. Incidence of bleeding requiring admission or hospital/office evaluation related to the injection procedure

Demographic data: collected from the EMR for secondary analyses

1. Age
2. Race
3. Body mass index (BMI)
4. OAB diagnosis at the time of procedure – OAB with vs OAB without urinary incontinence
5. Number of total BTX-A procedures
6. Past medical history
7. Past surgical history
8. Chronic narcotic use
9. 3 or more symptomatic UTI in the last year
10. Anticoagulation use

Sample Size Calculation and Statistical Methods:

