- The sample size was calculated by powering to the primary outcome of procedural discomfort as rated on the NPS. Cohen effect sizes were used with a power of 80%. The calculation accounted for a potential subject dropout rate of 20%. Three categorical variables (two degrees of freedom) will be utilized – Low discomfort vs. moderate discomfort vs. high discomfort – with a Chi-squared statistical analysis.
- Utilizing the above methods and an effect size of 30%, our target sample size will be 135 patients in total split between the two study groups.
- Variables will be defined as following on the NPS:
 - Low discomfort – 0-2
 - Moderate discomfort – 3-6
 - High discomfort – 7-10

Standard Practices and Considerations based on FDA recommendations for BTX-A:

1. Antiplatelet medications will be held for 72 hours prior to the procedure and can be restarted on the day after injection
2. Antibiotic prophylaxis will be prescribed for the day before, day of, and day after the procedure

Encounter 1

Scheduled visit for 100 units
intradetrusor BTX-A

10 mL/10 injections
vs.
5 mL/5 injections

- Consent obtained and patient completes OAB-qSF
- Randomization → Reconstitution of BTX-A in 10 mL vs 5 mL (patient blinded) → Patient rates discomfort from 0-10 on NPS → BTX-A injected → patient rates discomfort from 0-10 on NPS

Encounter 2

Telephone call at 30 days post
procedure

[figure not shown]
Data Collected from EMR:

- Demographic data → Age, Race, BMI, PMH, PSH, narcotic use, recurrent UTI, anticoagulation use
- Procedural data → UTI since procedure, Urinary retention requiring catheterization

- OABq-SF completed again
- Overall satisfaction since procedure assessed via standardized telephone script

Study Intervention

- The patients will be randomized into one of two treatment groups. In each of these groups, a different volume of normal saline will be used to reconstitute (dissolve) the BTX-A. The same injection volume (1 mL) will be utilized between groups, leading to a different number of total injections between groups
- Group A: 100 units BTX-A reconstituted in 5 mL normal saline, injected into the bladder in 5 separate injections of 1 mL. One injection will be at the trigone
- Group B: 100 units BTX-A reconstituted in 10 mL normal saline, injected into the bladder in 10 separate injections of 1 mL. One injection will be at the trigone

- Anatomic definitions:
 - Ureteral orifice: opening of ureter into the bladder

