Standard methods to protect privacy will be maintained. The identities of study subjects will remain confidential. Only the PI, primary co-investigator, and study coordinator will have access to the names of the participants. All consent forms and randomization allocations will be stored in a locked cabinet in the study coordinators password-protected HMH office. Any electronic data will be securely stored in the primary co-investigator's ([name]) office on a password protected office computer. This office is always locked and the computer is only opened through password protection. All data will be stored in Houston Methodist's electronic record keeping system RedCap for organization and analyses. All physical data/consents will be destroyed (shredded or erased from the computer hard drive) when use is no longer needed but not before a minimum of 3 years of data collection.

Informed Consent Documentation and Process

- Informed consent will be obtained from a member of the research team on the day of the BTX-A Procedure
- Patients undergoing intradetrusor BTX-A within the Urogynecology or Urology offices at HMH TMC, West, or Willowbrook will be identified the week prior and all subjects meeting criteria for inclusion will be approached about participation on the day of their scheduled procedure. If the subject fulfills inclusion criteria, the study team member (attending, fellow, research coordinator) will discuss the goal of the study and the process of BTX-A reconstitution and injection. If the patient is interested, the study requirements will be explained in detail - including requirements on the day of the procedure (short questionnaire, NPS rating prior to and after procedure) and 4 week follow up telephone call. The patient

will be given appropriate time to answer any questions she may have related to the study. Written information will be provided and the physician will allow adequate time for the subject to reflect flowing this discussion.

- If the patient agrees to participate, they will be consented in person by a member of the research team and will then be randomized. These documents will be safely stored as discussed above.
- A copy of the consent will be retained by the research coordinator in a locked file cabinet, and one copy will be given to the patient.

Waiver of Informed Consent and/or Authorization

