A screening waiver will be requested preparatory for research (waiver requested for feasibility, recruiting, access to charts, pre-screening). We are not requesting a waiver of informed consent.

The waiver of HIPPA Authorization will be required given the following:

- Requirement for the ability to screen patients for eligibility for the study to the absolute minimum extent required. It will not be feasible to conduct this research without the ability to screen for recruiting given that eligible patients will need to be identified prior to their scheduled procedure. The risk of this waiver only lies within the small possibility of loss of confidentiality that is inherent to any chart review for the purposes of academic study. These risks will be minimized by the measures described below.
- The data extracted from the EMR from the selected patient population will satisfy the objectives of this research which include evaluating discomfort related to BTX-A injections, peri-procedural factors and outcomes, and patient characteristics that may predict treatment satisfaction and response. The data that will be extracted from the EMR is listed in the Study Design portion of this document. We will extract the minimum information required to complete this study. We will not be able to satisfy the primary objectives of this research without the collection of demographic information, procedural details, and procedural outcomes that will be charted in the EMR.
- Security measures will be taken to assure that PHI will not be subject to improper use. All physical study data (consents, OABq-SF forms) will be kept in a locked cabinet inside a locked office that belongs to the primary researcher. Electronic information will be maintained in a password-protected database (RedCap). Only the researchers will have access to this data and it is password protected within the system.
- The procedural risk of this research is minimal. We will be studying a procedure via two techniques that are considered to be standard of care and are routinely performed in our office. We will not be introducing any study medications – the patients will receive 100 units BTX-A regardless of whether they choose to accept or decline enrollment into the study. The risk of a loss of confidentiality related to the collection of PHI is minimal due to the above mentioned safety precautions.

References

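### As described, 30-day complications rest on the EMR alone, so events treated elsewhere may count as no event; the planned call could ask about them

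*Combined protocol and SAP*

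**What the plan says.** Specific Aims/Purpose makes the comparison of complication rates between the two groups a secondary aim. Secondary Outcomes, items 3 to 5, name the complications:

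- UTI: "Symptomatic urinary tract infection (UTI) within the first 30 days after the procedure will be recorded". The definition needs a positive dip or culture plus a symptom.
- Catheterisation for bothersome incomplete emptying, also with a 30-day limit.
- Bleeding: "Incidence of bleeding requiring admission or hospital/office evaluation related to the injection procedure". No time limit is given.

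On the source of these data, the Encounter 1 / Encounter 2 outline has a block headed "Data Collected from EMR", and its procedural entry reads "Procedural data → UTI since procedure, Urinary retention requiring catheterization". The section on waiver of consent and authorization likewise speaks of "procedural outcomes that will be charted in the EMR", and refers to the Study Design portion for the list of extracted items.

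The one later contact is Encounter 2, "Telephone call at 30 days post" procedure. Its described content is a second OAB-q SF and "Overall satisfaction since procedure assessed via standardized telephone script". Informed Consent Documentation and Process calls the same contact a "4 week follow up telephone call".

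**The concern.** No visit is planned after the procedure. A UTI or a catheterisation therefore reaches the data only if the woman seeks care that is charted in the system's own record. If she goes to an urgent-care clinic, an outside hospital or her own doctor, the record may show nothing, and in the data that looks the same as no event. No section describes asking patients about complications or care elsewhere, or obtaining outside records.

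Incomplete capture of this kind would lower the complication rates that the trial reports. Even if equal in both arms, it would shrink the absolute difference between them. It would thus make the two techniques look both safer and more alike than they are, in a comparison the plan sets out to make.

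**Working it through.** **The plan's own figure.** The sample size serves the primary outcome only. Inputs from Sample Size Calculation and Statistical Methods: effect size w = 0.30, 2 degrees of freedom, power 80%, dropout 20%. Alpha is not stated; 0.05 is assumed. The noncentral chi-square gives N = 107.05, rounded up to 108, and 108 / 0.8 = 135. This reproduces the target exactly and does not depend on the present point. The plan gives no expected rate or power for the complication comparisons.

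**Effect of incomplete capture on rates.** Let p be the true rate and s the share of events that reaches the EMR. Observed rate = s × p. True rates are taken from Risks to Subjects (UTI up to 10-30%, retention up to 5%). The values of s are assumptions, since the documents give none.

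| Outcome | True rate | Expected events in 135 | Observed, s = 90% | s = 70% | s = 50% |
|---|---|---|---|---|---|
| UTI, low end | 10% | 13.5 | 9% | 7% | 5% |
| UTI, high end | 30% | 40.5 | 27% | 21% | 15% |
| Catheterisation | 5% | 6.8 | 4.5% | 3.5% | 2.5% |

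**Effect on the comparison.** With equal s in both arms, the observed difference is s × (p1 − p2), while the ratio (s × p1) / (s × p2) = p1 / p2 is unchanged. As an illustration only, a true difference of 10 points is seen as 9, 7 or 5 points at s = 90%, 70% or 50%.

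**Bleeding.** Risks to Subjects puts bleeding that needs admission below 1%. At 1%, 135 × 0.01 = 1.35 events are expected, and the chance of seeing none is 0.99^135 = 0.26. The outcome also takes in office or hospital evaluation, so its rate may be higher. With so few events, one missed case can turn a reported rate into zero.

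**The opposite error for UTI.** The UTI outcome accepts urinary frequency or urgency as the symptom without requiring a change from baseline. The UTI exclusion criterion in Study Population does require one. All participants have OAB, so a positive dip with their usual symptoms could count as a UTI. If a share f of unaffected women is falsely counted, the observed rate is s × p + f × (1 − p). This equals p when f = p(1 − s) / (1 − p). At s = 80%:

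- p = 10%: 0.10 × 0.20 / 0.90 = 2.2%
- p = 20%: 0.20 × 0.20 / 0.80 = 5.0%
- p = 30%: 0.30 × 0.20 / 0.70 = 8.6%

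A modest false-positive share would thus cancel the loss in the overall UTI rate. This symptom wording is not part of the catheterisation or bleeding outcomes.

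**The case against.** Several stronger readings are tempting, and the documents do not support them.

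- *Events are being missed and rates are understated.* A reader might take this as fact. The documents say nothing about how much care happens elsewhere or what outside information the EMR holds. The telephone script is not reproduced, and a figure beside the encounter outline is not shown. Under-capture is a risk, and for UTI even its net direction is uncertain.
- *Bleeding will not be collected at all.* It is secondary outcome 5, and the waiver section refers to the Study Design portion, which contains that list. The procedural entry in the outline also omits procedure time, which is to be recorded, so it is probably a summary. What stands is that bleeding has no explicit source, no time window and no place in that entry.
- *A call at 4 weeks cuts the 30-day window short.* It does not while UTI and catheterisation come from the EMR. The timing matters only once the call is used to find events.
- *The loss of power can be calculated from 10% versus 30% UTI.* With 67 per arm and two-sided 0.05, that contrast gives 83% power, falling to 65% at 70% capture. But the 10-30% is a literature range that the protocol attributes to differing UTI definitions, and nothing suggests a threefold difference between techniques. At 10% versus 20%, power is only 37% even with full capture (26% at 70%). The comparison was never powered, so power is not the measure of this problem.
- *The plan is built to show equal complications for a new technique.* The hypothesis concerns less discomfort with maintained efficacy, and both techniques are described as standard and routine.

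None of this answers the central point: the only stated source is passive, and a contact with every patient is already planned.

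**Conclusion.** The point holds as a risk to a stated secondary aim. Followed as written, the plan may count UTI, catheterisation and bleeding treated outside the system as no event. The observed rates and the absolute difference between arms would then shrink in proportion to capture, by 10% to 50% over the assumed range of 90% to 50% capture. The true size is unknown. The scaling assumes equal capture in both arms and, for UTI, no offsetting false positives.

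If the unseen script already asks about complications, what remains is to say so and to name the source and window for each outcome. The primary outcome and N = 135 are unaffected. The change should be made because it is cheap and improves the safety comparison; the trial does not fail without it.

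**What to change.** 1. Add three fixed questions to the existing call, for every patient in both arms, each covering care received elsewhere: any UTI diagnosed or treated, any catheter use for incomplete emptying, any bleeding that led to a visit or admission.
2. Request outside records for positive answers.
3. Count catheterisation and bleeding if found by either call or EMR. Count UTI as the outcome only when the dip or culture criterion in Secondary Outcomes is met. Report treated UTI without an obtainable result separately or in a sensitivity analysis. A telephone report alone cannot satisfy the UTI definition.
4. State a 30-day window for bleeding and add it to the procedural data in the encounter outline.
5. Reconcile the call timing in the encounter outline (30 days) and in the consent section (4 weeks) so that the call falls on or after day 30 and covers the whole window.

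Cost: about a minute more per call and a few record requests. The sample size does not change.

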Design: This will be a single-blinded, parallel randomized control trial (RCT) utilizing two study arms. This trial will be designed and reported as outlined in the CONSORT guidelines.¹³

Recruitment: Female patients scheduled to undergo injection of 100 units of intradetrusor BTX-A for the treatment of idiopathic overactive bladder will be identified through the electronic medical record (EMR). **This is the standard of care/standard dosing for the treatment of OAB and we will recruit and sample from patients who are already scheduled for this therapy prior to study enrollment.** Idiopathic OAB will be defined as “urinary urgency, with or without urgency urinary incontinence, usually accompanied by urinary frequency and nocturia, in the absence of urinary tract infection or other obvious pathology” and without evidence of neurogenic bladder.¹ These patients will be approached on the day of the procedure and consented in person if they are interested in participating.

Study Groups: The patients will be randomized to one of two groups:

- 100 units BTX-A reconstituted in 5 mL normal saline, injected into the bladder in 5 separate injections of 1 mL. One injection will be at the trigone
- 100 units BTX-A reconstituted in 10 mL normal saline, injected into the bladder in 10 separate injections of 1 mL. One injection will be at the trigone

Each of these methods of BTX-A injection into the bladder are considered to be standard of care and are performed routinely in our daily practice.

Randomization:

- Eligible and consenting subjects will be randomized with equal probability of assignment (1:1) to one of the two study arms (5 mL/5 injections vs 10 mL/10 injections). Randomization will occur on the day of the procedure immediately after consent.
- The randomization schedule will be generated using the NIH National Cancer Institute Clinical Trial Randomization Tool. Opaque folders with the study number, consent and envelope-sealed randomized group allocation will be created by the primary co-investigator and will be stored in a locked cabinet. The randomized allocation will be opened by the attending physician after the study consent has been completed and the BTX-A will then be prepared for injection.

Blinding: This will be a single-blind RCT. The patients will be blinded to their treatment allocation but for practical purposes, the attending physician will not be blinded given that they will be performing the injections.

Primary Outcomes:

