Idiopathic OAB will be defined as “urinary urgency, with or without urgency urinary incontinence, and is usually accompanied by urinary frequency and nocturia, in the absence of urinary tract infection or other obvious pathology” and without evidence of neurogenic bladder.¹ These patients will be approached on the day of the procedure and consented in person if they are interested in participating. Other than a detailed consent form, no recruitment materials or advertisements will be utilized as part of this study.

Withdrawal of Subjects

- Subjects would be withdrawn from the study if they are found to have symptomatic urinary tract infection on the day of the procedure – this would be defined by symptoms such as dysuria, frequency or urgency above baseline, or hematuria along with a urine dip that is positive for nitrites or leukocyte esterase.
- Subjects would be withdrawn if they are not able to tolerate the procedure itself and it is terminated prior to full injection of reconstituted BTX-A or if BTX-A was not able to be injected for other reasons (difficult anatomy, unable to pass scope or perform in the office)

Provisions to Protect the Privacy Interests of Subjects

- Privacy will be protected by ensuring that the patient interacts with and discloses information to only essential members of the research team to maximize confidentiality
 - Caregivers that patients interact with during a typical BTX-A procedure include front desk staff for check in, the nurse/medical assistant helping with the procedure, a resident or fellow if present in clinic that day, and the attending staff.
 - Additional personnel patients would have to interact with to participate in the study would be a research member during the consent process ([name] - Fellow, [name], [name] - research coordinators) and a research member during the telephone follow-up ([name])
- The patient will be made to feel at ease with this research through a thorough explanation of the study protocol, the BTX-A procedure itself, and follow-up telephone encounter. All study members will be introduced by name and title and it will be well-explained that either injection protocol are standard ways that we perform BTX-A in the office every day.

Risks to Subjects

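### Randomised patients who cannot tolerate the procedure are withdrawn, and nothing keeps them in the analysis of discomfort or secures a pain score when the procedure stops

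*Combined protocol and SAP*

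**What the plan says.** All references are to the combined protocol and SAP.

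- Primary Outcomes: "The primary outcome of this study will be patient discomfort related to BTX-A injection". The NPS is rated before and after the injections, and "The measurement for comparison will be the difference in those values".
- Randomization: assignment follows consent on the day of the procedure. "The randomized allocation will be opened by the attending physician after the study consent has been completed", and only then is the drug prepared. The Encounter 1 flow and the Informed Consent section give the same order.
- Blinding: "the attending physician will not be blinded given that they will be performing the injections".
- Withdrawal of Subjects, second bullet: "Subjects would be withdrawn if they are not able to tolerate the procedure itself and it is terminated prior to full injection". The same bullet goes on: "or if BTX-A was not able to be injected for other reasons (difficult anatomy, unable to pass scope or perform in the office".
- Sample Size Calculation and Statistical Methods: a chi-squared test on three discomfort bands, 135 patients in total, and "The calculation accounted for a potential subject dropout rate of 20" per cent.
- Design: "This trial will be designed and reported as outlined in the CONSORT guidelines".

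**The concern.** The bullet takes out patients after randomisation for a reason that is nearly the primary outcome itself. A woman who cannot bear the injections is probably among those with the most discomfort. If she leaves the analysis, the worst experiences go with her, and they may go unequally: one arm has twice as many injections, and the physician performing them knows the allocation.

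The hypothesis is that fewer injections hurt less, so these are among the most informative observations in the trial. With no rule fixed in advance, whether to count these patients, and with what score, would be decided after the data are seen.

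The bullet also merges two different groups: patients stopped during the injections, who have had injection discomfort, and patients never injected, for whom injection discomfort does not exist.

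**Working it through.** **1. Order of events.** Consent, randomisation, opening of the allocation, reconstitution, NPS, injections, NPS. Anyone stopped for intolerance is therefore already randomised, and if injection has begun her baseline NPS is already due.

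**2. What covers her afterwards.** No section names an analysis population, says that withdrawn patients are analysed or replaced, calls for an NPS at stopping, or gives a missing-data rule. The nearest texts are the CONSORT commitment, which should lead to a count of withdrawals but names no analysis set or score, and the dropout allowance.

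**3. The plan's sample size.** Inputs from the document: effect size 0.30 (read as Cohen's w), 2 degrees of freedom, power 80%, dropout 20%. Alpha is not stated; 0.05 is assumed. The noncentrality is λ = N·w², and power is P(χ²₂(λ) > 5.991).

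- N = 108: λ = 108 × 0.09 = 9.72, power 0.804.
- 108 / (1 − 0.20) = 135, as stated.
- All 135 evaluable: λ = 135 × 0.09 = 12.15, power 0.887.

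The allowance thus restores the number evaluable. It does nothing about which patients are lost.

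**4. Illustration of outcome-dependent loss.** Stopping rates and category splits are assumptions; the documents give neither. The base is 135/2 = 67.5 per arm, because the allowance may already cover same-day withdrawals. Scores are latent normal, SD 3, cut at 2.5 and 6.5, with arm means set so that w = 0.30. Low/moderate/high, 5 versus 10 injections:

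- (a) centred at 3: 57.4/36.2/6.4% versus 30.2/49.0/20.8%
- (b) centred at 4: 43.9/44.2/11.9% versus 19.9/48.8/31.3%

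Stopped patients are removed either all from the high band, or half from high and half from moderate. The splits are then rescaled and λ = Σ over arms of n·Σ(p − p̄)²/p̄, where p̄ is the pooled share of each band.

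Example, split (a), 2% versus 8%, all from high:

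- 5 injections: high 6.4 − 2 = 4.4 out of 98, giving 58.6/36.9/4.5%, n = 67.5 × 0.98 = 66.15.
- 10 injections: high 20.8 − 8 = 12.8 out of 92, giving 32.8/53.3/13.9%, n = 67.5 × 0.92 = 62.10.
- λ = 9.66, w = √(9.66/128.25) = 0.274, power 0.801.

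Power, split (a) / split (b):

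| Stopped, 5 vs 10 injections | All from high | Half from moderate |
|---|---|---|
| none | 0.887 / 0.887 | 0.887 / 0.887 |
| 1% vs 2% | 0.883 / 0.882 | 0.883 / 0.884 |
| 2.5% vs 5% | 0.878 / 0.873 | 0.877 / 0.878 |
| 2% vs 8% | 0.801 / 0.807 | 0.829 / 0.845 |
| 5% vs 5% | 0.946 / 0.927 | 0.916 / 0.906 |

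- At 2.5% vs 5% (67.5 × 0.025 = 1.7 and 67.5 × 0.05 = 3.4 patients), w stays at 0.30, so the small fall is only lost numbers.
- At 2% vs 8% (1.4 and 5.4 patients), w falls to 0.27-0.29. Losing the same number at random (N = 128, w = 0.30) would leave power at 0.869, so most of the fall comes from who is lost. The gap in the high band narrows from 14.4 to 9.4 points in (a) and from 19.4 to 15.2 in (b) if all come from high, or to 12.7 and 18.6 if half do.
- With 2% stopped in the 5-injection arm, power drops below 80% only at about 9% in the other arm (all from high) or about 10-13% (half from moderate).
- Equal 5% loss raises w to 0.32-0.34. The top of that range is extreme: in (a) it removes 5/6.4 = 78% of high-discomfort women in the 5-injection arm and 5/20.8 = 24% in the other.

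One limit applies throughout. The model bands a single 0-10 score. The before-after difference is not modelled, because no baseline distribution is given.

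**The case against.** **Withdrawn need not mean excluded.** A reader might infer that the plan orders these patients out of the analysis. It does not say so: an NPS after injection is scheduled, and nothing says it is skipped or discarded when injection is cut short. This stands. The point is that the plan does not keep them either, and the usual sense of withdrawal would remove them.

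**Stopping is probably rare.** The protocol describes the therapy as usually well tolerated, local anaesthetic is instilled, and pain syndromes are excluded. At low rates the effect is negligible, and even at 2% versus 8% power stays at or above the planned 80%. This also stands, and it limits the weight of the point. But the documents give no stopping rate, so rarity cannot be confirmed from them.

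**False positives.** A reader might infer that the rule inflates the type I error. In a null simulation (60,000 trials, 2% versus 8% stopped, all from the high band) rejection was 17% centred at 3 and 10% centred at 4. With 12.2% or 20.2% of women in the high band, that means stopping 8/12.2 = 66% or 8/20.2 = 40% of high-discomfort women in one arm, against 2/12.2 = 16% or 2/20.2 = 10% in the other, although discomfort is identical in both. With half drawn from moderate, rejection is 6-7%. Nothing in the documents supports the extreme case, so it should carry no weight.

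**CONSORT and the dropout allowance.** Neither settles the matter, for the reasons given in the working.

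**Conclusion.** The point holds and should be fixed. The plan withdraws randomised patients for a reason closely tied to the primary outcome, and no text retains them or secures their score. If withdrawal is applied in its usual sense, the loss depends on the outcome and may differ by arm.

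The size is unknown. Under the assumed splits, rates and alpha of 0.05, it is negligible when stopping is rare and matters only with a steep imbalance, where it uses up most or all of the margin above 80% power. The direction is not fixed either: heavier stopping in the 10-injection arm hides a difference, while equal stopping can enlarge it. The documents therefore do not support a claim that the trial is biased towards one arm or underpowered. They support the narrower conclusion that a foreseeable, outcome-related loss has no rule, and that a cheap rule would remove most of it.

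**What to change.** Amend the second withdrawal bullet and add a short analysis-set statement:

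1. Every patient in whom injection has begun stays in the study and is analysed in her randomised arm. This is the primary analysis set.
2. If the procedure is stopped, an NPS is recorded then and serves as her post-injection value. The 30-day call is kept.
3. If no rating is obtained, it is missing in the primary analysis. One prespecified sensitivity analysis places her in the worst discomfort category. Imputing 10 minus her baseline should be avoided: with a baseline of 8 it gives 10 − 8 = 2, which falls in the low band (0-2) if the difference is what is banded.
4. Patients stopped before any injection are reported separately by arm and given no injection-discomfort score.
5. All early terminations are reported by arm, with the reason and the number of injections given.

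The cost is protocol wording, one extra NPS entry with a reason code, and one short sensitivity analysis. The target of 135 and the clinical decision to stop are unchanged. Two limits remain: the primary set still leaves out patients never injected, and the decision to stop is made by an unblinded physician. That is why items 4 and 5 are reported by arm.
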